14.5.5.2 Simulation parameters

500 trials were used to simulate each scenario and the total minimum number of DLT to control the declaration of MTD was fixed to one.

The maximal dose to jump to was orthogonal and follows the protocol specifications (Section 10.4.2.1 of the protocol):

Table 14- Preference matrix

LGX818 – QD (mg)	MEK162 - BID (mg)			
	15	30	45	60
50	1	2	3	4
100	2	3	4	5
150	3	4	5	6
200	4	5	6	7
250	5	6	7	8
300	6	7	8	9
350	7	8	9	10
400	8	9	10	10
450	9	10	10	10

The number of patients to enroll in each cohort and stopping rules used to declare MTD were defined as:

- Minimum cohort size: 3
- Minimum number of patients enrolled: 18
- Maximum number of patients enrolled: 60
- Minimum number of patients enrolled at a given dose combination in order to declare MTD: 6

14.5.5.3 Metrics

Operating characteristics were reviewed for the simulations to compare the relative performance under each true scenario. The metrics reviewed were:

- I. Average proportion of patients receiving a target dose combination on study (I)
- II. Average proportion of patients receiving a dose combination with true $P(DLT) \geq 35\%$ on study (II)
- III. Average proportion of patients receiving a dose combination with true $P(DLT) < 16\%$ on study (III)
- IV. Probability of recommending a target dose combination as the MTD (correct final decision) (IV)
- V. Probability of recommending a dose combinations with true $P(DLT) \geq 35\%$ as the MTD (patient risk) (V)
- VI. Probability of recommending dose combination with true $P(DLT) < 16\%$ as the MTD (VI)

14.5.5.4 Results

Table 14-23 presents the model for the 5 different scenarios studied, additionally showing how many of the trials were stopped before declaring MTD when all dose combinations were considered too toxic.

Table 14- Results

Scenario	Metric						
	I	II	III	IV	V	VI	Stopped
1	0.681	0.035	0.286	0.882	0.016	0.076	0.026
2	0.532	0.147	0.32	0.716	0.126	0.122	0.036
3	0.552	0.099	0.35	0.78	0.046	0.136	0.038
4	0.474	0.155	0.273	0.496	0.382	0.088	0.034
5	0.613	0.133	0.252	0.736	0.152	0.058	0.054

In summary, the simulated operating characteristics show:

- (Metric IV) that the identified MTD falls within the targeted interval in more than 72% of the cases, except for scenario 4.
- (Metric V) that on average, less than 15% of patients are treated at overly toxic doses, excluding scenario 4.
- (Metric I) The average proportion of patients receiving a target dose combination on study is 47% to 68%.
- Scenario 4 needs careful consideration, since the true underlying probability of DLT (15.7%) for the combination MEK162 60mg + LGX818 50mg is very close to the lower boundary of the targeted toxicity [16%, 35%). Unsurprisingly, this combination is therefore identified relatively often as an MTD. Had this combination been counted as a correct MTD as well, then metric IV improves to 56.8%.

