10.8 Sample size calculation

Phase Ib

Dose escalation: Cohorts of 3 to 6 evaluable patients will be enrolled in the dose escalation part including at least six patients at the MTD/RP2D level, as described in [Section 6.2.4](#).

Multiple cohorts may be sequentially enrolled to the same dose level. Additional cohorts of 1 to 6 patients may be enrolled at any dose level below the estimated MTD/RP2D for further elaboration of safety and PK parameters as required. At least 18 patients are expected to be treated in the dual-combination dose-escalation part of the study, for the model to have reasonable operating characteristics relating to its MTD recommendation (see [Appendix 5](#) for details). At least 12 patients are expected to be treated in the triple-combination dose-escalation part of the study.

Phase II

Arm 1 dual combination: Based on the prior distribution and decision rules described in [Section 10.4](#), it was explored how likely it is to wrongly declare activity given the true DCR = 20%, and how likely it is to correctly declare activity given the true DCR = 40%, when 28 patients are evaluated.

- If the true DCR = 20%, the probability to wrongly declare activity (i.e. seeing at least 9 patients with SD or better) is 9.0%.
- If the true DCR = 40%, the probability to correctly declare activity (i.e. seeing at least 9 patients with SD or better) is 85.2%.

If 9 out of 28 patients have at least SD or better, then the posterior risk of the true DCR being in the unacceptable category is 7.0%.

Note: if the interim analysis is performed, the probability to correctly declare activity if the true DCR = 40% is 82.3%.

Arm 2 dual combination: Based on the prior distribution and decision rules described in [Section 10.4](#), it was explored how likely it is to wrongly declare activity given the true ORR = 10%, and how likely it is to correctly declare activity given the true ORR = 20%, when 41 patients are evaluated:

- If the true ORR = 10%, the probability to wrongly declare activity (i.e. seeing at least 7 responses) is 11.0%.
- If the true ORR = 20%, the probability to correctly declare activity (i.e. seeing at least 7 responses) is 73.9%.

If 7 out of 41 patients have PR or CR, then the posterior risk of the true ORR being in the unacceptable category is 9.8%.

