14.5.5 Simulated operating characteristics

14.5.5.1 Hypothetical scenarios

In order to show how the Bayesian combination model reacts, the following hypothetical scenarios were investigated:

- Scenario 1: no increases in odds of DLT, i.e., the simulation parameter values for the BLRM are set to the mean values of the prior.
- Scenario 2: is scenario 1 + 50% increase in odds of DLT, i.e., 50% increase in odds of DLT.

- Scenario 3: is scenario 1 + 100% increase in odds of DLT, i.e., 100% increase in odds of DLT.
- Scenario 4: is scenario 1 but with constant interaction across doses.
- Scenario 5: is scenario 2 but with constant interaction across doses.

Scenarios 4 and 5 represent stress tests since the underlying interaction is assumed constant across doses and not dose-dependent (as assumed in the model).

Table 14-17 True underlying probabilities of DLT for Scenario 1

LGX818 -QD (mg)	MEK162 - BID (mg)			
	15	30	45	60
30	0.035	0.039	0.06	0.126
50	0.076	0.081	0.103	0.169
100	0.203	0.213	0.239	0.304
150	0.331	0.349	0.38	0.443
200	0.445	0.469	0.504	0.564
250	0.539	0.568	0.606	0.662
300	0.615	0.648	0.686	0.737
350	0.676	0.711	0.749	0.795
400	0.725	0.761	0.797	0.839
450	0.765	0.8	0.835	0.872

Bold values indicate dose combinations in the targeted toxicity interval [16%, 35%)

Table 14-18 True underlying probabilities of DLT for Scenario 2

LGX818 -QD (mg)	MEK162 - BID (mg)			
	15	30	45	60
30	0.036	0.041	0.066	0.141
50	0.08	0.089	0.118	0.2
100	0.22	0.249	0.298	0.396
150	0.366	0.421	0.491	0.594
200	0.495	0.57	0.651	0.744
250	0.601	0.686	0.767	0.844
300	0.684	0.772	0.845	0.904
350	0.748	0.833	0.896	0.941
400	0.798	0.877	0.93	0.963
450	0.837	0.909	0.952	0.977

Bold values indicate dose combinations in the targeted toxicity interval [16%, 35%)

Table 14-19 True underlying probabilities of DLT for Scenario 3

LGX818 -QD (mg)	MEK162 - BID (mg)			
	15	30	45	60
30	0.037	0.043	0.07	0.151
50	0.083	0.095	0.13	0.224
100	0.232	0.277	0.345	0.466
150	0.391	0.474	0.572	0.692
200	0.531	0.639	0.742	0.838
250	0.643	0.758	0.849	0.917
300	0.729	0.839	0.912	0.957
350	0.793	0.892	0.948	0.978
400	0.841	0.927	0.969	0.988
450	0.876	0.95	0.981	0.994

Bold values indicate dose combinations in the targeted toxicity interval [16%, 35%)

Table 14-20 True underlying probabilities of DLT for Scenario 4

LGX818- QD (mg)	MEK162 - BID (mg)			
	15	30	45	60
30	0.035	0.038	0.058	0.121
50	0.075	0.078	0.097	0.157
100	0.196	0.198	0.215	0.267
150	0.316	0.319	0.333	0.377
200	0.422	0.424	0.436	0.474

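### The Scenario 4 row of Table 14-23 cannot be right as printed: metrics I to III sum to 0.902, and V = 0.382 with VI = 0.088 does not follow from the stated model

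*Protocol*

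**What the plan says.** Section 10.8 justifies the minimum of 18 dual-combination escalation patients as needed "for the model to have reasonable operating characteristics relating to its MTD recommendation", and points to Appendix 5.

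Section 14.5.5.3 defines six metrics. I, II and III are the average proportions of patients treated at a target dose, an overly toxic dose (true DLT rate 35% or more) and an under-dose (below 16%). IV, V and VI are the probabilities that the declared MTD falls in those same three classes. V is the one marked as patient risk.

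In Section 14.5.5.4 the Scenario 4 row (I, II, III, IV, V, VI, stopped) reads "4 0.474 0.155 0.273 0.496 0.382 0.088 0.034". The text explains it by the 60/50 combination, whose true rate lies just under the 16% boundary: "Unsurprisingly, this combination is therefore identified relatively often as an MTD". It adds "Had this combination been counted as a correct MTD as well, then metric IV improves to 56.8" (per cent). A summary bullet labelled Metric V states that "on average, less than 15% of patients are treated at overly toxic doses, excluding scenario 4".

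**The concern.** The text and the table tell different stories about Scenario 4. The text blames a combination just below target. Choosing it would raise VI and lower IV. The table shows the opposite: VI is small, and V, the patient-risk metric, is by far the highest of the five scenarios. The treated-patient proportions in the same row do not add up either.

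This table is the evidence offered for the escalation design. A reader who takes the row at face value concludes that, under constant interaction, the design names a too-toxic MTD in more than a third of trials. If the row is wrong, that conclusion is wrong, and the error the design actually tends to make there, stopping slightly too low, goes unreported.

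**Working it through.** **1. Row sums (Table 14-23).** I+II+III must equal 1 up to rounding, and so must IV+V+VI+stopped.

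| Scenario | I+II+III | IV+V+VI+stopped |
|---|---|---|
| 1 | 0.681+0.035+0.286 = 1.002 | 0.882+0.016+0.076+0.026 = 1.000 |
| 2 | 0.532+0.147+0.320 = 0.999 | 0.716+0.126+0.122+0.036 = 1.000 |
| 3 | 0.552+0.099+0.350 = 1.001 | 0.780+0.046+0.136+0.038 = 1.000 |
| 4 | 0.474+0.155+0.273 = **0.902** | 0.496+0.382+0.088+0.034 = 1.000 |
| 5 | 0.613+0.133+0.252 = 0.998 | 0.736+0.152+0.058+0.054 = 1.000 |

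Row 4 loses 9.8% of patients, so at least one of I to III is wrong. The second sum is intact, but it would also be intact if V and VI had been exchanged.

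**2. Text against table.** The 60/50 sentence implies that this combination was declared in 0.568 − 0.496 = 0.072 of trials. That fits inside the printed VI of 0.088. It explains only 7.2 points of the fall in IV from Scenario 1 (0.882 − 0.496 = 0.386) and leaves the 38.2% in V without any explanation.

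**3. The scenario's truth is reproduced.** With the Table 14-14 means and no interaction, at LGX818 50 mg and MEK162 60 mg (reference doses 100 and 60 mg):
- LGX818: odds = exp(−1.415) × 0.5^exp(0.463) = 0.2429 × 0.3324 = 0.0807, so p = 0.0747.
- MEK162: odds = exp(−2.326) = 0.0977, so p = 0.0890.
- Combination: 1 − (1 − 0.0747)(1 − 0.0890) = 0.157.

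This is the last entry of the Table 14-20 row "50 0.075 0.078 0.097 0.157".

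**4. Re-simulation.** The 5-parameter model was fitted by importance sampling from the Table 14-14 prior. It reproduced eleven rows of Table 14-24 to about 0.005; for example, hypothetical scenario 9 there gave 0.554/0.202 against 0.552/0.203 printed. Trials started at 45/50 and escalated one partner by at most 100%. The overdose limit was 25%. An MTD needed at least 6 patients at the dose, 18 in total and 1 DLT, with a maximum of 60 patients. The runs used 250 to 1,000 trials per setting.

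The selection rule is not fully fixed. Section 10.4.2.1 takes the highest target probability, while Section 14.5.5.2 adds a preference matrix with tied scores. The tie matters here: MEK162 60/LGX818 50 and MEK162 45/LGX818 100 both score 4, and in Table 14-20 the first is an under-dose (0.157) and the second is on target (0.215). The check therefore varied the selection rule, tie-break, diagonal moves, cohort size, MEK162 doses and minimum sample size.

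| Scenario 4 | Printed | Re-simulated, all variants at the 25% limit |
|---|---|---|
| V | 0.382 | at most about 0.09 |
| VI | 0.088 | about 0.24 to 0.72 |
| 60/50 declared | 0.072 (implied) | about 0.18 to 0.64 |

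Monte Carlo error does not bridge this. The standard error of 0.382 in 500 trials is √(0.382 × 0.618/500) = 0.022, and of 0.09 in 250 trials √(0.09 × 0.91/250) = 0.018. The gap of 0.292 is more than ten times the combined 0.028. Loosening the overdose limit to 35% gave V = 0.11, and to 50% gave 0.23 to 0.26.

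**5. The 56.8%.** One run with ties broken toward LGX818 and cohorts of 3 had IV = 0.596 and 60/50 declared in 0.226 of trials. Counting 60/50 as correct gives 0.822. A run with diagonal moves gives 0.538 + 0.336 = 0.874.

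**6. Possible exchange of V and VI.** Another run with ties toward LGX818 gave IV 0.528, V 0.08, VI 0.36 and stopped 0.032. The printed row with V and VI exchanged is 0.496, 0.088, 0.382 and 0.034.

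**7. Other rows.** Re-simulated V brackets the printed value in rows 1, 2, 3 and 5 (0.00–0.06, 0.06–0.13, 0.03–0.07 and 0.05–0.18 against 0.016, 0.126, 0.046 and 0.152). VI does not in row 5 (0.14–0.26 against 0.058), and perhaps not in row 3 (0.16–0.23 against 0.136).

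**8. Summary bullets.** The claim that IV exceeds 72% outside Scenario 4 fails narrowly in Scenario 2 (71.6%). The bullet labelled Metric V describes patients treated, which is Metric II. For II it is true (maximum 0.147 outside Scenario 4). Metric V itself is 15.2% in Scenario 5.

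**The case against.** Several points on the other side stand.

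- A reader might argue from the tables alone that V cannot rise, because every combination in Scenario 4 is no more toxic than in Scenario 1. That does not follow. Scenario 3 is more toxic than Scenario 2, with the same overly toxic set on the simulated grid, yet V falls from 0.126 to 0.046. Lower toxicity permits more escalation. The comparison is a plausibility check only.
- A reader might infer that the protocol presents the design as an overdosing one. The documents do not go that far. The prose names 60/50, a combination slightly below target, and Section 14.5.5.1 calls Scenario 4 a stress test outside the model's interaction assumption. The overdosing impression comes from the printed V and from the bullet that sets Scenario 4 aside.
- A reader might infer that only Scenario 4 is affected, or that re-simulated values can replace the row. Neither holds. VI is also off in row 5, and IV for Scenario 4 ranged from about 0.40 to 0.69 depending on the rule.
- The 7.2-point gain is arithmetically compatible with the printed VI; it fails only against re-simulation.
- The consequence is limited. Recommended Phase II doses for the dual combination are already declared, enrolment is closed, and escalation also rested on clinical review.

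None of this rescues the 0.902 sum, or a V of 0.382 against at most about 0.09.

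**Conclusion.** The Scenario 4 row is wrong as printed. The 0.902 sum shows this without any simulation. The V and VI entries do not follow from the written model, the 25% overdose rule and Table 14-20: V is overstated by about 0.29 or more, and VI is understated by at least about 0.15 (0.24 − 0.088). The attribution to 60/50 therefore agrees with the model but conflicts with the table, and the 56.8% is not reproduced.

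An exchange of V and VI is the best-fitting explanation. It remains an inference, and it repairs neither the row sum nor the 56.8%. On the re-simulation, the main error in this stress test is recommending a dose slightly below target, not overdosing.

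The simulation findings assume the Table 14-14 prior and the stated stopping rules. The direction held under every selection rule tried; the exact values did not. This is a reporting error in evidence that Section 10.8 relies on, not a fault shown in the escalation design itself.

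**What to change.** 1. Re-extract Scenario 4 from the sponsor's simulation output, or re-run it, and state the selection and tie-break rule used.
2. Correct the row so that I to III sum to 1 and V and VI stand in the right columns. Recompute the 56.8% sentence from the same output. Use the sponsor's own figures, not values from any single re-simulated variant.
3. If the output confirms it, state that the main error in this scenario is recommending a dose slightly below target.
4. Check VI in rows 3 and 5 against the same output.
5. Relabel the Metric V bullet as Metric II, report Metric V separately (15.2% in Scenario 5), and change the Metric IV bullet to 71.6% or more.

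The cost is one re-extraction or re-run, one table row and a few sentences in Appendix 5. Section 14.10.1 confirms that enrolment is closed, so no patient or procedure is affected. The correction can be carried into the final clinical study report.

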14.5.6 Hypothetical dose escalation scenarios

In order to show how the Bayesian model reacts, different hypothetical dose escalation scenarios were investigated (Table 14-24). The design should make reasonable dose recommendations during the clinical trial based on the observed DLTs. During the study, the decision to dose escalate after completion of a given cohort and the actual dose chosen for the subsequent cohort will depend on the recommendation of the BLRM per EWOC principle and medical review of available clinical and laboratory data.

It is assumed for most scenarios that each cohort has exactly 3 evaluable patients. Scenario 20 illustrates the ability for the model to handle cohorts of different size. Dose escalation follows the rule listed in Section 6.2.4.

Overall, in the early cohort scenarios, the model is showing appropriate behaviors, in agreement with clinical sense and decision-making process: progressive increase of the combination doses if no DLT is observed (e.g., scenarios 1, 4, 10), staying at the same dose level and opening of a new cohort at the same dose combination when 1 DLT is reported (e.g., scenario 2), and decrease when more than 1 DLT is reported in a cohort (e.g., scenarios 5,6).

Table 14-24 Hypothetical dose escalation scenarios

Scenario	Dose combination MEK162 / LGX818	Npat	Ntox	Next dose combination (NDC)	P(Target) NDC	P(over) NDC	Median DLT rate (NDC)
1	45/50	3	0	60/50	0.279	0.096	0.119
2	45/50	3	1	45/50	0.398	0.232	0.211
3	45/50	3	2	stop			
4	45/50 45/100	3 3	0 0	60/100	0.240	0.126	0.107
5	45/50 45/100	3 3	0 1	45/50	0.224	0.034	0.084
6	45/50 45/100	3 3	0 2	45/50	0.308	0.095	0.123
7	45/50 45/100 45/50	3 3 3	0 1 0	45/100	0.397	0.243	0.214
8	45/50 45/100 45/50	3 3 3	0 1 1	45/50	0.407	0.064	0.152
9	45/50 45/100 45/50	3 3 3	0 1 2	45/50	0.552	0.203	0.237
10	45/50 45/100 60/100	3 3 3	0 0 0	60/150	0.158	0.204	0.084
11	45/50 45/100 60/100	3 3 3	0 0 1	60/100	0.399	0.185	0.189
12	45/50 45/100 60/100	3 3 3	0 0 2	45/100	0.480	0.241	0.238
13	45/50 45/100 45/150	3 3 3	0 0 0	45/200	0.154	0.115	0.058
14	45/50 45/100 45/150	3 3 3	0 0 1	45/100	0.310	0.040	0.121
15	45/50 45/100 45/150	3 3 3	0 0 2	45/100	0.432	0.135	0.181
16	45/50 45/100 45/150 45/100	3 3 3 3	0 0 2 0	60/100	0.375	0.177	0.179
17	45/50 45/100 45/150 45/100	3 3 3 3	0 0 2 1	45/100	0.542	0.169	0.222
18	45/50 45/100 45/150 45/100	3 3 3 3	0 0 2 2	45/50	0.283	0.042	0.105

Scenario	Dose combination MEK162 / LGX818	Npat	Ntox	Next dose combination (NDC)	P(Target) NDC	P(over) NDC	Median DLT rate (NDC)
19	45/50	3	0	60/300	0.076	0.115	0.011
	45/100	3	0				
	60/100	3	0				
	60/150	3	0				
20	45/50	3	0	60/100	0.467	0.083	0.174
	45/100	3	0				
	60/100	3	0				
	60/150	6	3				

14.5.7 Power for analysis of key secondary variables

Not applicable.

14.6.1 Statistical Model

Refer to Section 10.4.2 for the form of the model. Note that the 10 parameter model for the triple combination (LGX818+MEK162+LEE011) is an extension of 5 parameter model used for the dual combination (LGX818+MEK162). When the dose of LEE011 equals to 0, the 10 parameter model reduces to the existing 5 parameter model.

The Bayesian approach requires the specification of prior distributions for the model parameters. $((\log(\alpha_1), \log(\beta_1)), (\log(\alpha_2), \log(\beta_2)), (\log(\alpha_4), \log(\beta_4))), \eta_{12}, \eta_{14}, \eta_{24}, \eta_{124}$

The prior information for parameters $(\log(\alpha_x), \log(\beta_x))$ (where $x=1, 2, 4$) come from prior available dose-DLT information of LGX818, MEK162 and LEE011.

14.6.2 Prior Specification

The prior derivation for the 5 parameter dual combo (LGX818+MEK162) model was described in the original protocol as shown in Appendix 5 (Section 14.5).

14.6.2.1 Prior distribution for $\log(\alpha_4), \log(\beta_4)$ (LEE011 single agent component)

For this trial, historical data from the ongoing study CLEE011X2101 (first-in-human LEE011 oncology study) were used to derive an informative prior for the $(\log(\alpha_4), \log(\beta_4))$ (see Table 14-25).

1. The informative bivariate normal prior for the model parameters $(\log(\alpha_4), \log(\beta_4))$ was obtained as follows:
 - The median DLT rate at the LEE011 reference dose (400 mg, 3 weeks on 1 week off) was assumed 1/10 i.e. $\text{mean}(\log(\alpha_4)) = \log(1/9)$.
 - A doubling in dose was assumed to double odds of DLT, i.e. $\text{mean}(\log(\beta_4)) = 0$.
 - The standard deviation of $\log(\alpha_4)$ was set to 2 and the standard deviation of $\log(\beta_4)$ to 1, which allows for considerably prior uncertainty for the dose-toxicity profile.

- The correlation between $\log(\alpha_4)$ and $\log(\beta_4)$ was set to 0.
2. Data from 53 patients (treated with LEE011 3 week on 1 week off) eligible for the dose determining set of the study [CLEE011X2101] were used to update the dose-toxicity profile (See Table 14-25).

Three percentiles (2.5, 50, 97.5) of the posterior distribution are used to find the 5 parameters of the bivariate-normal distribution that is in best agreement with the percentiles for each dose level.

3. Heterogeneity between the historical and current study was incorporated by between-trial standard deviations and τ_{41} and τ_{42} for $\log(\alpha_4)$ and $\log(\beta_4)$. Both τ_{41} and τ_{42} were set to follow a log-normal distribution. Mean $\log(0.25)$ and standard deviation 0.01 was chosen for τ_{41} and mean $\log(0.125)$ and standard deviation 0.01 was chosen for τ_{42} which correspond to moderate between-trial variability.

Table 14-25 Data from CLEE11X2101

Dose of LEE011 (mg, 3 weeks on, 1 week off)	No of DLTs / No of evaluable patients
50	1/4
70	0/2
140	0/3
260	0/4
280	1/4
350	0/5
400	1/4
600	0/4
750	1/7
900	1/13
1200	2/3

Table 14-26 Prior, posterior and predictive distribution of ($\log(\alpha_4)$, $\log(\beta_4)$)

Parameter	Means	Standard deviations	Correlation
Prior for ($\log(\alpha_4)$, $\log(\beta_4)$)	($\log(1/9)$, 0)	(2, 1)	0
Normalized Posterior for ($\log(\alpha_4)$, $\log(\beta_4)$)	(-2.075, -0.744)	(0.396, 0.521)	-0.130
Predictive for ($\log(\alpha_4)$, $\log(\beta_4)$)	(-2.066, -0.749)	(0.527, 0.563)	-0.116

Interaction

As shown above, the distribution of η_{12} is inherited from existing LGX818 and MEK162 dual-combo model. A non-informative prior reflecting the current uncertainty about the toxicity of the combination treatment is used for η_{14} , η_{24} , η_{124} . There is no interaction expected between MEK162 and LEE011, we set the median of η_{24} to be $\log(1.02)$ which assumes a 2% increase of odds. This is a conservative way to set the prior. The 97.5 percentile of η_{24} is set to be $\log(2.2)$ which assumes a 1.2 fold increase of odds. LGX818 and LEE011 have potential positive interaction. Hence we set the median of η_{14} to be $\log(1.1)$ which assumes a 10% increase in odds of toxicity. The 97.5 percentile of η_{14} is set to be $\log(3)$, which assumes a 2 fold increase

of odds. We also set a conservative prior for 3 way interaction. The median of η_{124} is set to be $\log(1.02)$. The 97.5 percentile is set to be $\log(2.2)$.

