1.2.3.2 Clinical Study with LEE011

As of 4 February 2013, 56 patients have been treated with single agent LEE011 in the first-in human phase I study [CLEE011X2101] in which LEE011 is administered orally, once daily for 21 days followed by a 1 week rest (28-day cycle). Doses tested include 50 mg (n=4), 70 mg (n=2), 140 mg (n=4), 260 mg (n=4), 280 mg (n=4), 350 mg (n=5), 400 mg (n=5), 600 mg (n=4), 900 mg (n=13), 750 mg (n=8), and 1200 mg (n=3). In all, 8 DLTs have been observed. DLTs include grade 3 mucositis (n=1) in the 50 mg cohort, grade 3 pulmonary embolism (n=1) in the 280 mg cohort, grade 3 hyponatremia (n=1) and prolonged grade 3/4 neutropenia (n=1) in the 400 mg cohort, grade 4 thrombocytopenia (n=1) in the 750 mg cohort, grade 3 asymptomatic QTc prolongation with grade 3 neutropenia (n=1) in the 900 mg cohort and grade 4 febrile neutropenia (n=1) and grade 4 thrombocytopenia (n=1) in the 1200 mg cohort. The grade 3 mucositis observed in the 50 mg cohort was later determined to be due to herpes simplex virus (HSV) infection. A DLT related to mucositis has not been observed since. Four cases of Grade 1 or 2 mucositis have been observed in doses up to 350 mg; mucositis has not been observed at higher doses. The grade 3 pulmonary embolism was observed in a patient with NSCLC who

had diffuse bilateral lung disease and a central venous catheter. The grade 3 hyponatremia was asymptomatic and readily corrected with saline infusion. Grade 3 or 4 neutropenia and/or thrombocytopenia not meeting DLT criteria were seen in increasing frequency starting from 600 mg up to 1200 mg. Asymptomatic grade 1 or 2 QTc prolongation were observed in increasing frequency starting at 600 mg up to 1200 mg; 1 patient (25%) in the 600 mg cohort, 2 patients (25%) in the 750 mg cohort, 4 patients (31%) in the 900 mg cohort, and 3 patients (100%) in the 1200 mg cohort. The most frequently reported treatment-related AEs include fatigue, nausea, anemia, asthenia, neutropenia, vomiting, leukopenia, increased blood creatinine, decreased appetite, diarrhea, hypoalbuminemia, lymphocytopenia, myalgia, thrombocytopenia, dizziness, erythema, hyperglycemia, mucosal inflammation and stomatitis. The majority have been grades 1 or 2 and reversible.

The MTD of LEE011 for the 3 weeks on/1 week off schedule is 900 mg. The study continues with exploration of alternate dosing schedules and further assessment of safety, tolerability, and preliminary anti-tumor activity of LEE011.

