Following the principle of EWOC, after each cohort of patients the dose combination recommended by the BLRM is the one with the highest posterior probability of DLT in the target interval [16%, 35%) among the doses fulfilling the overdose criterion that there is less than 25% chance of excessive toxicity.

In addition, the maximum inter-cohort combined dose escalation across the 2 combination partners is limited to 100%, where 100% refers to the sum of the relative escalation for each of the combination partners, e.g. 100% and 0% increase for LGX818 and MEK162 respectively, 0% and 100% increase for LGX818 and MEK162 respectively, etc.

Summaries of the posterior distribution of model parameters and posterior distribution of DLT rates based on the DLT data from all patients enrolled in the study and included in the DDS will be produced.

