14.6.2.2 Summary

The prior distribution of the parameters is summarized in [Table 14-27](#). The prior distribution of the DLT rates for provisional doses is summarized in [Table 14-28](#). Note that the posterior probability of excessive toxicity of the proposed starting dose for triple combination (LGX818+MEK162+LEE011) is 10.2% which satisfies EWOC criteria.

Table 14-27 Prior distribution of model parameters

Parameter	Means	Standard deviations	Correlation
$(\log(\alpha_1), \log(\beta_1))$	(-2.917, -1.820)	(0.986, 1.041)	0.233
$(\log(\alpha_2), \log(\beta_2))$	(-2.326, 1.564)	(1.107, 1.368)	-0.535
$(\log(\alpha_4), \log(\beta_4))$	(-2.066, -0.749)	(0.527, 0.563)	-0.116
η_{12}	0	1.528	NA
η_{14}	0.095	0.512	NA
η_{24}	0.020	0.392	NA
η_{124}	0.020	0.392	NA

Table 14-28 Summary of prior distribution of DLT rates for triple combo (LGX818+MEK162+LEE011) including current DLT data (up to Apr 16, 2013) from dual combo (LGX818+MEK162)

LEE011 (mg, 3 week on, 1 week)	Prior probabilities that Pr(DLT) is in interval			Mean	SD	Quantiles		
	[0.0, 0.16)	[0.16, 0.35)	[0.35, 1.00]			2.50%	50.00%	97.50%
MEK162 45mg BID, LGX818 450mg QD								
100	0.662	0.236	0.102	0.149	0.145	0.006	0.102	0.551
200	0.552	0.216	0.232	0.218	0.226	0.004	0.132	0.809
400	0.468	0.14	0.392	0.337	0.341	0.001	0.194	0.986
600	0.44	0.098	0.462	0.411	0.396	0	0.265	0.999
800	0.428	0.075	0.498	0.455	0.424	0	0.342	1
MEK162 45mg BID, LGX818 600mg QD								
100	0.632	0.204	0.164	0.174	0.195	0.002	0.097	0.72
200	0.543	0.169	0.288	0.253	0.281	0.001	0.129	0.926
400	0.472	0.106	0.423	0.373	0.381	0	0.202	0.998
600	0.447	0.073	0.481	0.439	0.423	0	0.291	1
800	0.434	0.056	0.51	0.476	0.443	0	0.39	1

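### The LEE011 prior rests on 7 DLTs (1/4 at 400 mg) where the background section reports 8 (two at 400 mg), and the protocol does not explain the difference

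*Protocol*

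**What the plan says.** Section 1.2.3.2 describes the first-in-human LEE011 study: "As of 4 February 2013, 56 patients have been treated with single agent LEE011". It continues with "In all, 8 DLTs have been observed" and lists the events by cohort, among them "grade 3 hyponatremia (n=1) and prolonged grade 3/4 neutropenia (n=1) in the 400 mg cohort".

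Section 14.6.2.1 takes the same study as the source of the LEE011 single-agent prior and updates a weak prior with "Data from 53 patients (treated with LEE011 3 week on 1 week off) eligible" for its dose-determining set. Table 14-25 lists the counts by dose, with 1 DLT in 4 evaluable patients at 400 mg.

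The resulting predictive distribution (Table 14-26) goes into Table 14-27 and from there into Tables 14-28 and 14-29. Section 14.6.2.2 concludes that "the posterior probability of excessive toxicity of the proposed starting dose for triple combination (LGX818+MEK162+LEE011) is 10.2" per cent. The decision rule in Section 10.4.2.1 admits a dose combination only if "there is less than 25% chance of excessive toxicity".

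**The concern.** Two sections of one protocol give different DLT counts for the same study, and the lower count feeds the safety model. The difference is confined to 400 mg, which is also the reference dose, so it acts directly on log(alpha4).

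The notation in Section 1.2.3.2 points to two patients at 400 mg. At 900 mg, two findings in one patient are joined under a single n=1. At 1200 mg the text reads "grade 4 febrile neutropenia (n=1) and grade 4 thrombocytopenia (n=1) in the 1200 mg cohort", the same form as at 400 mg, and Table 14-25 counts that pair as 2/3.

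The overdose rule is a hard limit, and several printed probabilities lie just under it (0.232 in Table 14-28; 0.227, 0.229 and 0.242 in Table 14-29). A small change in the prior could therefore alter what the tables show as admissible.

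**Working it through.** **1. Counts side by side.**

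| LEE011 dose (mg) | Treated, Section 1.2.3.2 | DLTs, Section 1.2.3.2 | DLTs/evaluable, Table 14-25 |
|---|---|---|---|
| 50 | 4 | 1 | 1/4 |
| 70 | 2 | 0 | 0/2 |
| 140 | 4 | 0 | 0/3 |
| 260 | 4 | 0 | 0/4 |
| 280 | 4 | 1 | 1/4 |
| 350 | 5 | 0 | 0/5 |
| 400 | 5 | 2 | 1/4 |
| 600 | 4 | 0 | 0/4 |
| 750 | 8 | 1 | 1/7 |
| 900 | 13 | 1 | 1/13 |
| 1200 | 3 | 2 | 2/3 |
| Total | 56 | 8 | 7/53 |

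Both sources add up internally. Three patients leave between treated and evaluable (one each at 140, 400 and 750 mg). One DLT leaves, at 400 mg.

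**2. Which count entered the prior.** The model is logit(pi4) = log(alpha4) + beta4·log(d/400). The weak prior has means (log(1/9), 0), SDs (2, 1) and correlation 0. The posterior was computed on a grid, and a bivariate normal was fitted to the 2.5, 50 and 97.5 percentiles, as Section 14.6.2.1 describes.

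- With 1/4 at 400 mg: means (-2.075, -0.779), SDs (0.412, 0.551). Table 14-26 prints (-2.075, -0.744) and (0.396, 0.521).
- With 2/4: means (-1.901, -0.835).
- Direct posterior means of log(alpha4): -2.06 with 1/4, -1.89 with 2/4, and -1.91 with 2/5.

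The printed prior therefore used 1/4. On the probability scale at 400 mg, 1/(1 + e^2.075) = 0.11 becomes 1/(1 + e^1.901) = 0.13.

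**3. Reproducing the printed overdose probabilities.** For the triple combination, with x = dose/reference dose and q = (1 - pi1)(1 - pi2)(1 - pi4), the odds of a DLT are exp(eta12·x1·x2 + eta14·x1·x4 + eta24·x2·x4 + eta124·x1·x2·x4)·(1 - q)/q. Excessive toxicity is a DLT rate of at least 0.35.

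Sampling Table 14-27 alone gives 0.453 at the starting combination, against the printed 0.102. The dual-combination DLT data named in the title of Table 14-28 are therefore essential, but their counts are not printed. They have to be assumed. The Amendment 4 rationale gives 35 treated patients.

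One set that fits is 6, 6, 4, 4, 8 and 7 patients at LGX818 50, 100, 200, 400, 450 and 600 mg, with one DLT, at 600 mg. It recovers eight printed Table 14-28 values to within 0.005. A second set, 0/25 at 50 to 450 mg and 1/8 at 600 mg, fits about as well and gives scenario 3 as 0.227 to 0.229 (printed 0.227).

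**4. Adding a second 400 mg DLT (2/4).** Recomputed values under the first set, then the printed value plus the range of shifts found across the runs:

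| Quantity | Printed | Recomputed, 1/4 to 2/4 | Printed + shift |
|---|---|---|---|
| Start: LEE011 100, LGX818 450, MEK162 45 mg | 0.102 | 0.102 to 0.122 | 0.120 to 0.123 |
| LEE011 200 mg, before triple data | 0.232 | 0.228 to 0.250 | 0.252 to 0.254 |
| Table 14-29 scenario 3, next dose 50 mg | 0.227 | 0.233 to 0.275 | 0.260 to 0.268 |

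If the fifth treated patient is added instead (2/5), the printed-plus-shift values are 0.118 to 0.120, 0.250 to 0.252, and about 0.25 to 0.26.

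Across all assumed dual data sets that fitted Table 14-28 to within 0.012, the recomputed 200 mg value with 2/4 ran from 0.244 to 0.263, so it can fall on either side of the limit. Some of these sets put DLTs at 400 and 450 mg and none at 600 mg. They give scenario 3 as only 0.16 to 0.18 before the change, well short of the printed 0.227, and so were discounted. Their shift is similar (about 0.036 to 0.037).

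**5. Other scenarios in Table 14-29.** Scenario 1 moves from 0.106 to 0.114, scenario 4 from 0.218 to 0.226, scenario 10 from 0.227 to 0.223, scenario 12 stays at 0.239, and scenario 14 moves from 0.235 to 0.229. None crosses 0.25.

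**The case against.** The strongest objection is that no error has been shown. Section 1.2.3.2 describes all treated patients at a stated date. Table 14-25 is undated and restricted to another study's dose-determining set, whose rule is not printed. At 400 mg patients and DLTs both fall by one, which is the pattern left by excluding one patient with a DLT. Section 10.1.3 of this protocol admits patients who met the exposure minimum or stopped early because of a DLT; read literally, a patient with a DLT who did neither would be left out.

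This stands as a possibility. Against it, Section 6.2.4.2 makes a DLT in the first cycle sufficient for evaluability, so exclusion would be unusual if the LEE011 study worked the same way. Later reclassification is a weaker explanation: the 50 mg mucositis was afterwards attributed to a viral infection, yet Table 14-25 still counts it.

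The second objection concerns consequence. Section 6.2.2 requires the model to be updated with the latest LEE011 data before the first triple-combination patient is dosed, and enrolment has closed (Section 14.10.1). Scenario 3 is a hypothetical illustration, and the 200 mg row before any triple data drives no decision, because escalation starts at 100 mg. All of this stands and limits the weight of the point. It does not explain the missing DLT or correct the printed tables. Section 10.4.2.1 still calls for posterior DLT summaries, and Section 10.4.2.2 reuses the model for the Phase II re-assessment.

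A reader might infer that the starting combination fails the overdose criterion, or that two tabulated values clearly exceed 25%. The documents support neither: the starting combination stays near 12%, and the 200 mg value only reaches the limit.

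**Conclusion.** The inconsistency is established from the printed text and needs no model: 8 DLTs against 7, differing only at 400 mg, with no reason stated. Its cause is not established. It may be an omitted DLT, a patient with a DLT excluded from the LEE011 study's dose-determining set, or two events in one patient, though the notation makes the last unlikely. Table 14-25 adds up correctly, and the printed posterior follows from it.

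The effect is conditional. If a second patient with a DLT belongs in the set, one illustrative recommendation (scenario 3) moves clearly past the 25% limit, one pre-data row lands on it, and the starting-dose conclusion is unchanged. The shift in log(alpha4) needs only the printed data. The overdose probabilities also rest on assumed dual-combination counts, so they should be read as approximate.

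**What to change.** Check the 400 mg records of the LEE011 study and reconcile Section 1.2.3.2 with Table 14-25.

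- If two evaluable patients had DLTs at 400 mg: correct the table, rerun the LEE011 posterior and predictive prior, and reissue Tables 14-26 to 14-29 and the 10.2% statement. Carry the corrected input into the model update of Section 6.2.2 and every later BLRM run, including the posterior summaries for the final report.
- If one of the patients was not in the dose-determining set, or both events were in one patient: state in Section 14.6.2.1 why one 400 mg DLT is not counted, and make Section 1.2.3.2 agree.

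Printing the dual-combination counts used for Table 14-28 would let readers check the result. The cost is one data check and, only in the first case, a model rerun, after which some stated overdose probabilities would be less favourable.
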